STUDY DESIGN	This is a non-interventional, multi-center, open-label, controlled study to identify and characterize the epigenetic signatures for a set of hematological malignancies.
OBJECTIVES	
Primary Objectives:
 
 1. Biomarker discovery - define a set of differential epigenetic biomarkers that uniquely identify the following conditions: MM, pre-MM conditions (SMM and MGUS), HL, aggressive NHL (DLBCL), FL, MZL, AML, MDS subjects at risk and control subjects with no malignant disease. 2. Validation – validating the discovery platform (HemaChip) as a diagnostic tool for various hematological malignancies. 3. Towards early detection – Selected patients tested periodically to evaluate early relapse detection capability of the HemaChip. 4. Towards population screening - evaluate the sensitivity and specificity for screening in populations at risk for developing the investigated cancers: (i) elderly (>65 years old) at high risk

	
to develop MM; (ii) first-degree relatives of the conditions described above.
 
Secondary Objectives:
 
 1. Evaluate the correlation between epigenetic status and well-known prognostic markers, including known genetic markers. 2. Predict response to therapy. 
Exploratory Objectives:
 
 1. Identify new therapeutic targets based on epigenetically modified genomic loci. 2. Provide prognostic information at pre-treatment and monitoring of minimal residual disease (MRD).

METHODOLOGY
	
Subjects will be screened for eligibility and then, after signing an Informed Consent Form, the first peripheral blood sample will be obtained.
 
Periodical blood samples will be obtained from the participants. Relapse patients will have their retrospective blood samples analyzed to identify early signs of disease.
 
The first stage (discovery phase) will include at least 30 patients from each of the following groups: MM, pre-MM conditions (SMM and MGUS), HL, aggressive NHL (DLBCL), FL, MZL, AML, , MDS and control subjects with no malignant disease.
 
In the second stage, at least 250 patients with MM and 250 patients with NHL and at least 100 patients with each of the remaining hematological malignancies mentioned above will be tested. Out of these patients, AML, lymphoma and MM patients will be followed-up at the clinical sites. Periodic sampling will be defined according to disease type and progression rate. Blood and plasma samples will

	
be stored in the clinical sites until relapse diagnosis. At this stage, blood samples will be analyzed retrospectively on the HemaChip. The screening, enrollment and blood collection can begin in the first stage of the trial, in order to allow a maximum follow-up period for at-risk subjects as part of the study, and to meet the recruitment goals.
 
The last stage consists of the screening of a larger group of subjects at risk to develop MM / lymphoproliferative disorder. This stage will include 400 elderly patients (>65 years old) and 500 first-degree relatives of patients (and in particular siblings). The screening, enrollment and sample collection can begin in the first stage of the trial, in order to allow a maximum follow-up period for at-risk subjects as part of the study, and to meet the recruitment goals.
 
In all stages, the age and sex-matched subgroups will be considered and matched.
 
During the follow-up period, demographic and baseline parameters including sex, age, race, height and weight, medical history, smoking status, details of initial diagnosis and treatment history, concomitant medications as well as adverse events (AEs) of special interest (see section 9.1), (serious) AEs related to study procedures, treatment for the disease, disease response and survival status will be collected (as applicable).

STUDY PERIOD	Recruitment and follow-up period: 36 months
POPULATION SIZE	
First stage: at least 300 subjects
 
Second stage: at least 1000 subjects

	Third stage: up to 900 subjects

MAIN INCLUSION CRITERIA
	
General criteria for all study population :
 
 1. Male and female subjects ≥ 18 years of age 2. Ability to understand and willingness to sign a written informed consent document. 
For Patients with hematological malignancies:
 
 1. Patients who have been diagnosed, have measurable disease and / or are being monitored / followed-up due to one of the following conditions: MM, pre-MM conditions (SMM and MGUS), HL, aggressive NHL (DLBCL), FL, MZL, AML, MDS that did not yet undergo any treatment. 
NOTE: Patients diagnosed with DLBCL that is transformed from FL or MZL, and patients diagnosed with AML secondary to MDS or MPN, that were treated for their primary disease (FL/MZL/MDS/MPN) prior to study enrollment, are eligible.
 
For subjects at risk for developing the investigated hematological malignancies:
 
 1. First-degree relatives; 2. Elderly subjects ≥ 65 years of age.

MAIN EXCLUSION CRITERIA
	
 1. Patients/subjects with current co-diagnosis of another type of cancer; 2. Patients/subjects with a known active or prior cancer (other than defined as study population), occurring within the last 2 years (even if considered to be in complete remission). Patients/subjects with non-melanoma skin cancer or carcinoma in situ of any type are not excluded if they have undergone complete resection;

	
 3. Patients/subjects with active inflammatory autoimmune disease that requires treatment with immunosuppressive/immunomodulation agents; 4. Patients/subjects with known human immunodeficiency virus (HIV) positive; 5. Patients/subjects with known active Hepatitis A/B/C or past hepatitis C; 6. Subjects that are likely to be noncompliant with the protocol, or felt to be unsuitable by the investigator for any other reason.

DURATION OF SUBJECT PARTICIPATION
	
Subjects that serve as controls, subjects at risk (from the Third stage) and a subset of patients from the First and Second stage are expected to donate blood a single time. Following this donation, their participation will end.
 
For a subset of patients, it is expected, after signing the informed consents, that the serial samplings will be performed during the disease follow-up according to the standard clinical practice and/or recommended schedule and disease assessment plan (see Table 3).
 
For enrolled subjects, all have the right to withdraw at any time.
 
All follow-up patients will be followed for a period of up to 36 months.
 
Subjects who complete the main study, may be followed up for their disease status, anti-cancer treatments, concomitant medications, new primary malignancy and survival, following a statistical review of the study results. Serial blood samplings will be performed during the long-term follow-up according to the standard clinical practice and/or recommended schedule and disease assessment plan (see Table 3).

	
A detailed plan for long-term follow-up beyond the main study will be provided as an amendment to this protocol.

EVALUATIONS
	
Classification of a broad spectrum of haematological malignancies based on the detection of epigenetic biomarkers from genomic DNA, cell-free (cf) DNA, exosomal DNA, RNA and non-coding RNA. The identified biomarkers will include proteins, metabolites, and other characteristic biomolecules.
 
Year 1: During the discovery phase, all tests will be conducted by JaxBio and TAU with the aid of technical service providers. At this stage, microarray measurements will be performed on a commercial platform that will be purchased from suppliers such as Agilent / Illumina. All reagents needed for the test will be either purchased or produced in-house.
 
Years 2-3: Throughout the second phase of the project, a custom-targeted microarray, HemaChip will be developed and used for all tests. The HemaChip and custom reagents will be distributed to partners’ labs and all tests will be conducted at the clinical sites and partners labs. Additional validation tests will be conducted by JaxBio and TAU, as needed.


STATISTICAL CONSIDERATIONS
	
All subjects meeting the eligibility criteria who signed a consent form and donated at least one blood sample will be considered evaluable for analysis.
 
All data collected will be summarized and presented. Continuous variables will be described as the mean, median, standard deviation and range of n observations. Categorical data will be described with contingency tables including frequency and percentage. Individual patient listings will be generated and presented. We used an initial sample size determination for binomial distribution (arcsine transformation, significance level = 0.05, test power = 0.8). Based

	
on previous experiments, we propose two estimates – expected target sensitivity, and minimum acceptable sensitivity. Estimate of the expected target sensitivity of the discovery chip was set to 95%. This estimate sets the minimum acceptable limits for establishing statistical tests and represents the best expected result. The second estimate sets the minimum acceptable sensitivity of the discovery chip to 89%. The value is based on reported literature and the fact that this phase is conducted on diagnosed patients with active disease. With these parameters, a minimum sample size of 30 samples/indication is needed. This should be revisited upon accumulation of data.
 
Statistical descriptions and analyses will be carried out using SPSS and in-house statistical analysis software.

INTERIM ANALYSIS
	
A single formal interim comparative analysis of the epigenetic patterns in blood-derived DNA from control subjects with no malignant disease and subjects at risk for developing the investigated hematological malignancies and the patterns obtained for all malignant and premalignant hematological conditions will be conducted after approximately 24 months from the beginning of the study and will include:
 
Comparative analysis for 250 newly diagnosed NHL samples with HemaChip
 
Comparative analysis for 250 newly diagnosed MM samples with HemaChip
 
Comparative analysis for 100 samples of the following conditions: SMM, MGUS, HL, AML, MDS, control subjects with no malignant disease and subjects at risk for developing the investigated hematological malignancies.


POWER AND SIGNIFICANCE LEVEL
	
The sample size of each stage of the clinical study will be determined in accordance with technology development requirements. Hence, three designs should be taken into account: Discovery stage performed with the discovery chip, and the validation and screening stages performed with targeted HemaChip. All the calculations have been made with optimistic assumptions that we will be able to prepare such sensitive chips that classify the studied hematological malignancies types with expected target sensitivity of above 95%. Moreover, the minimal sensitivity of 80% was set as a lower bound for all statistics to get a scale for the further Sample Size calculation. Importantly, based on incidences of particular diseases the calculated Sample Size will include significant proportions of all diseases of interest.

--	--

TABLE OF CONTENTS

PROTOCOL SYNOPSIS	5
LIST OF ABBREVIATIONS	16
1 BACKGROUND AND STUDY RATIONAL	18
1.1 HemaChip mechanism of action	20
1.2 The consortium and JaxBio	21
2 STUDY OBJECTIVES	22
3 ENDPOINTS	23
4 STUDY DESIGN	23
4.1 First stage (discovery phase)	23
4.2 Second stage	23
4.3 Third stage	24
4.4 Clinical follow-up	24
4.4.1 Recommended follow-up schedule	25
5 STUDY POPULATION	25
5.1 Number of subjects	25
5.2 Eligibility	27
5.2.1 Inclusion criteria	27
5.2.2 Exclusion criteria	27
5.3 Subject screening and registration	28
5.4 Subject withdrawal criteria	28
5.5 Enrollment restrictions	29
6 DESIGN & TREATMENT PLAN	29
6.1 Duration of participation	29
6.2 Schedule of events	29
6.2.1 Unscheduled visits	35
6.2.2 Response assessment	35
7 STUDY ASSESSMENTS	35
7.1 Screening period	35
8 HEMACHIP	37
9 REGULATORY AND REPORTING REQUIREMENTS	38
9.1 Adverse event definition	38

9.2	Adverse events of special interest	38
9.3	Serious adverse event definition	38
9.4	Adverse events reporting	39
9.5	Medical monitoring and safety management	40
10	STATISTICAL CONSIDERATIONS.....	40
10.1	Study design	40
10.2	Statistical methods.....	40
10.2.1	Study populations.....	41
10.2.2	Demographic and baseline parameters	41
10.3	Interim analysis	41
10.4	Sample size and power calculation	42
10.5	Criteria for termination of the trial.....	44
10.6	Procedure for accounting for missing, unused and spurious data	45
11	ADMINISTRATIVE ASPECTS.....	45
11.1	Contract research organization	45
11.1.1	Communication between sites and CRO	45
11.2	Study conduct	45
11.3	Quality control by the monitoring team	45

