As evident from Figure 1, the larger the deviation of the observed sensitivity from the 80% value, the smaller the sampling size required to prove that the actual sensitivity of the tested discovery array is statistically significantly higher than 80%. In case of the optimistic estimate, it is expected the sensitivity of the chip designed for the disease detection to be 95%, which corresponds to a minimum sample size of 30 subjects for each disease subtype. In the context of the mentioned numbers, and the confidence level of 95%, the confidence interval will be 0.817, and 0.999. In case of the minimum acceptable estimate, the sensitivity of the discovery array is set to be 89%, which corresponds to a sample size range of about 99 subjects per disease. In the context of the mentioned numbers, and the confidence level 95%, the confidence interval will be 0.810, and 0.943.

Since the real sensitivity of the discovery is unknown and based on experience with 60,000 pixel arrays, we have decided to start with a set of 30 subjects and use the data for more precise and evidence based power calculation. The selection of the biomarker panel may be performed even under this uncertainty by including also more variable markers in the HemaChip panel and further tune the array once sufficient data has been accumulated.

Validation stage:

The large discovery chip serves as a matrix for selecting significant markers and as an experimental platform for the final targeted HemaChip design with a reduced number of spots/markers. Here, the same statistics need to be performed to prove that the HemaChip will work with a high statistical accuracy. Since there has been a reduction in markers, we will assume that the sensitivity of the chip will be at a lower level, yet still above the minimum threshold of 80%. With the same test setup (arcsine transformation, significance level = 0.05, test power = 0.8) and the expected specificity of 85% (lower bound), approximately 356 subjects (Sample size) will be needed to verify the results. In the context of the mentioned numbers, and the confidence level 95%, the confidence interval will be 0.810, 0.887 (Figure 12).

The research program is designed to test diagnosed ~250 subjects of MM and NHL, and 100 subjects of the remaining conditions in the validation stage. If the selection of biomarkers was sufficiently good, the expected sensitivity of the HemaChip will not dramatically decline relative to

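### The synopsis derives 30 per indication from 95% and 89%, but Section 10.4 gets it from 95% against 80% with an unstated one-sided test, and the interval quoted for n=30 cannot occur at n=30

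*Protocol*

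**What the plan says.** The Statistical considerations row of the synopsis gives the method as "arcsine transformation, significance level = 0.05, test power = 0.8". It names two sensitivities: "Estimate of the expected target sensitivity of the discovery chip was set to 95" per cent, and "The second estimate sets the minimum acceptable sensitivity of the discovery chip to 89" per cent. It then concludes: "With these parameters, a minimum sample size of 30 samples/indication is needed", and adds that this should be revisited as data accumulate. That row mentions no third value.

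The Power and significance level row of the synopsis says that "the minimal sensitivity of 80% was set as a lower bound for all statistics". Section 10.4 repeats this and gives the aim of the test as "to prove that the actual sensitivity of the tested discovery array is statistically significantly higher than 80" per cent. Its table lists 30 at an expected sensitivity of 0.95 and 99 at 0.89. The text pairs the 95% case with 30 subjects per disease subtype and says "the confidence interval will be 0.817, and 0.999". For the other case it says that "the sensitivity of the discovery array is set to be 89%, which corresponds to a sample size range of about 99 subjects per disease", with an interval of 0.810 to 0.943. Section 10.4 then explains that, because the real sensitivity is unknown, the study starts with 30 and will use the data for a better power calculation. The protocol does not say whether the test is one-sided or two-sided.

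**The concern.** The synopsis sentence credits 30 to a pair of values that did not produce it. A reader who takes it at face value will believe that 30 patients per indication give 80% power in relation to the 89% minimum acceptable sensitivity. Section 10.4 shows otherwise. The value that matters is 80%, and 89% leads to 99 there.

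Two details make the statement harder to check. The significance level has no sidedness, and the table depends on it. The interval printed with n=30 also does not belong to that sample size. Sensitivity is part of the primary endpoints (Section 3), and 30 per group sets first-stage enrolment (Section 4.1 and Table 1). The planned recalculation of power needs a stated null value and sidedness to start from.

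**Working it through.** **Inputs.** Arcsine method, alpha 0.05, power 0.80 (synopsis and Section 10.4); target 95% and minimum acceptable 89% (synopsis and Section 10.4); lower bound 80% (synopsis, Power and significance level, and Section 10.4).

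**Formula.** For one proportion, n = ((z_alpha + z_power)/h)², with h = 2·asin(√p1) − 2·asin(√p0). Here z_power = 0.8416, and z_alpha = 1.6449 one-sided or 1.9600 two-sided.

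**The plan's own figures, null 80%.**
- True 95%: h = 2.6906 − 2.2143 = 0.4763. One-sided n = (2.4865/0.4763)² = 27.3, so 28 (printed 30). Two-sided n = 34.6, so 35.
- True 89%: h = 2.4655 − 2.2143 = 0.2512. One-sided n = 98.01, so 99 (printed 99). Two-sided n = 124.4, so 125.
- True 85%: one-sided 355.4, so 356 (printed 356). Two-sided 451.2, so 452.
- True 84%: one-sided 568.75, so 569 (printed 569). Two-sided 722.04, so 723.

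Thirteen of the 14 table rows equal the one-sided result rounded up. The 95% row is printed two patients higher. The two-sided results do not fit. The table is therefore a one-sided 5% test against 80%.

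**Is 30 adequate for that test?** Exact binomial, n=30: P(X ≥ 28 | 0.80) = 0.044, so at least 28/30 is required. P(X ≥ 28 | 0.95) = 0.812. At n=28 at least 27/28 is required, and power at 95% is only 0.588. So 30 gives the stated 80% power by the exact test, and 28 would not.

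**What 30 gives at 89%.** As the true sensitivity against 80%, arcsine power is Φ(0.2512·√30 − 1.6449) = 0.39, and exact power is P(X ≥ 28 | 0.89) = 0.344.

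**If 89% were the null.** h = 2.6906 − 2.4655 = 0.2251. One-sided n = 122.01, so 123. Two-sided n = 154.9, so 155. Power at n=30 would be 34% one-sided by the arcsine formula. By the exact test it would be 21%, because only 30/30 passes.

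**The interval.** Exact (Clopper-Pearson) two-sided 95% limits:

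| Result | 95% interval |
|---|---|
| 27/28 | 0.8165 to 0.9991 |
| 28/30 | 0.779 to 0.992 |
| 29/30 | 0.828 to 0.999 |
| 88/99 | 0.810 to 0.943 |

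The printed 0.817 to 0.999 matches 27/28 and neither neighbouring result at n=30. The same method reproduces the interval printed for n=99.

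**Test against interval.** 28/30 passes the one-sided test, yet its two-sided 95% interval contains 0.80. The one-sided 95% lower bound for 28/30, which is the lower limit of the two-sided 90% interval, is 0.805 and agrees with the test.

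**The case against.** The strongest defence is that the synopsis is only condensed. The 80% bound stands in its next row and is declared to apply to all statistics, and Section 10.4 says plainly that the test is against 80%. Section 10.4 also discloses that the 89% case needs about 99, calls its assumptions optimistic and presents 30 as a starting size. Section 5.5 allows sample numbers to rise. No decision rule at 80% or 89% is attached to the discovery stage, whose main purpose is marker selection.

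Much of this stands. It limits the consequence and shows that nothing is hidden in Section 10.4. It does not make the synopsis sentence correct, because on neither use of 89% does that value lead to 30. Nor does it supply the missing sidedness or make the printed interval attainable.

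A reader might infer three stronger conclusions, and the documents support none of them:
- That 30 should have been 123. That requires 89% as the null. The synopsis wording invites this, but both documented statements of the comparator say 80%.
- That 30 is an error for 28. The arcsine formula gives 28, but 30 is the safer number by the exact test.
- That the real power is 55%, the chance of at least 29/30 at a true 95%. This assumes that success is read from the two-sided 95% interval, and the protocol states no such rule.

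**Conclusion.** The synopsis is wrong as written about where 30 comes from, and Section 10.4 quotes an interval that belongs to 28 patients. The sample size itself holds for the hypothesis in Section 10.4: 81% exact power against 80% at one-sided alpha 0.05 if true sensitivity is 95%. If true sensitivity is only 89%, power at n=30 falls to 34% (exact) or 39% (arcsine), and the protocol's own method asks for 99. Thirty patients do not test whether sensitivity reaches 89%. The interval error is small: the printed lower limit of 0.817 compares with 0.828 for 29/30 and 0.779 for 28/30.

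This rests on two inferences. The test is taken as one-sided because Section 10.4 speaks of exceeding 80% and because only one-sided values reproduce the table. The intervals are taken as Clopper-Pearson because that method matches the printed limits.

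**What to change.** Keep n=30. In the synopsis and in Section 10.4:

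1. State that 30 per indication gives about 80% power (exact 81%, at least 28/30) to show sensitivity above 80% at one-sided alpha 0.05 if true sensitivity is 95%.
2. State that if true sensitivity is 89%, power at n=30 is about 34% to 39% and 99 would be needed, and that n=30 does not test the 89% minimum.
3. Replace 0.817 to 0.999 with an interval attainable at n=30, such as 0.779 to 0.992 for 28/30 or 0.828 to 0.999 for 29/30, and name the result it refers to.
4. Report the one-sided 95% lower bound (two-sided 90% interval) alongside, so that the interval matches the test.

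The cost is protocol wording and a less favourable stated power at 89%. No patients are added.

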APPENDIX 6 – Proposed modified International Working Group response criteria for altering
natural history of MDS..... 65

LIST OF ABBREVIATIONS

AE	Adverse Event
AML	Acute Myeloid Leukemia
ASCT	Allogeneic Stem Cell Transplantation
cfDNA	Cell-Free DNA
CRF	Case Report Form
CRO	Clinical Research Organization
DLBCL	Diffuse Large B Cell Lymphoma
eCRF	Electronic CRF
FL	Follicular Lymphoma
FNOL	University Hospital Olomouc
FZMB	Forschungszentrum für Medizintechnik und Biotechnologie
GCP	Good Clinical Practice
HBV	Hepatitis B Virus
HCV	Hepatitis C Virus
HIV	Human Immunodeficiency Virus
HL	Hodgkin Lymphoma
ICF	Informed Consent Form
ICH	International Conference on Harmonization
IMWG	International Myeloma Work Group
IRB	Institutional Review Board
MedDRA	Medical Dictionary of Regulatory Activities
MDS	Myelodysplastic Syndrome
MGUS	Monoclonal Gammopathy of Undetermined Significance
MM	Multiple Myeloma
MRD	Minimal Residual Disease
MPN	Myeloproliferative Neoplasms
MZL	Marginal Zone Lymphoma
NHL	Non-Hodgkin Lymphoma
NKUA	National and Kapodistrian University of Athens
PCD	Plasma Cell Dyscracia
PCR	Polymerase Chain Reaction
PD	Progressive Disease
QPCR	Quantitative PCR
QA	Quality Assurance
SAE	Serious Adverse Event

SMM	Smoldering Multiple Myeloma
TAU	Tel-Aviv University
TASMC	Tel-Aviv Sourasky Medical Center
VULSK	Vilnius University Hospital Santaros Klinikos

